5.2 Pharmacokinetic properties

Absorption

Gastrointestinal absorption is rapid and complete.

Distribution

Distribution is rapid and is associated with a level of protein binding close to 94%, primarily to albumin.

Biotransformation

Tianeptine is extensively metabolised in the liver, primarily by beta-oxidation, without CYP450 involvement. Its primary metabolite, pentanoic acid (MC5), is active and less potent than tianeptine.

Elimination

The elimination of tianeptine is characterised by a short terminal half-life of 3 h with most metabolites excreted in the urine.

Elderly, very elderly and fragile patients

In elderly patients, plasma concentrations of tianeptine were increased by 30% and those of MC5 approximately doubled after single or repeated administration, in comparison with younger patients (see section 4.2).

In very elderly (87±5 years) or fragile (45±9 kg) patients, a significant increase in Cmax and exposure (area under the curve, AUC) to tianeptine and MC5 was observed after single administration (see section 4.2).

Patients with severe renal impairment (CRCL <19 ml/min)

The pharmacokinetics of tianeptine remain unchanged but exposure to MC5 is approximately doubled after single and repeated administration (see section 4.2).

Patients with severe cirrhosis (Child-Pugh score Class C)

Exposure to tianeptine and to MC5 after the administration of a single dose of 12.5 mg is increased compared to adult patients with depression (see section 4.2).

In cases of milder cirrhosis, such as patients with chronic alcoholism, the effects on pharmacokinetic parameters are negligible (see section 4.2).

5.3 **Preclinical safety data**

Non-clinical data from conventional genotoxicity and carcinogenicity studies have identified no specific risks for humans.

In the fertility study, an increase in preimplantation loss was observed at the maternally toxic dose of 45 mg/kg/day (12 times the human dose determined by body surface area).

Tianeptine is not teratogenic in rats and rabbits.

In the peri- and postnatal study, dysfunction in milk secretion and increased postimplantation and postnatal loss were observed in rats at the maternally toxic dose of 45 mg/kg/day (12 times the human dose determined by body surface area).

6. PHARMACEUTICAL PARTICULARS

6.1 List of excipients

Mannitol, corn starch, talc, magnesium stearate.

Coating: ethylcellulose, glycerol monooleate, SEPIFILM SE 700 White (polyvidone, carmellose sodium, colloidal anhydrous silica, talc, sucrose, polysorbate 80, titanium dioxide, sodium bicarbonate), white beeswax.

6.2 Incompatibilities

Not applicable.

6.3 Shelf life

36 months.

6.4 Special precautions for storage

No special precautions for storage (climate zones I and II).

Do not store at a temperature above 30°C (climate zones III and IV).

6.5 Nature and contents of container

28 or 100 tablets in blister packs (Aluminium/PVC) (climate zones I and II).

28 or 100 tablets in blister packs (Aluminium/PVC) overwrapped in sachets (climate zones III and IV).

6.6 Special precautions for disposal and handling

No specific requirements.

7. MARKETING AUTHORISATION HOLDER / EXPLOITANT

LES LABORATOIRES SERVIER

8. MARKETING AUTHORISATION NUMBER(S)

- 34009 267 223 5 7: 28 tablets in blister packs (Aluminium/PVC)
- 34009 558 336.0 4: 100 tablets in blister packs (Aluminium/PVC)
- 34009 267 224 1 8: 28 tablets in blister packs (Aluminium/PVC) overwrapped in sachets
- 34009 579 827 3 7: 100 tablets in blister packs (Aluminium/PVC), overwrapped in sachets.

9. DATE OF FIRST AUTHORISATION/RENEWAL OF THE AUTHORISATION

MA approved on 06/02/1987.

Renewed on 06/02/2012.

10. DATE OF REVISION OF THE TEXT

March 2018

11. GENERAL CLASSIFICATION FOR SUPPLY

List I.

Duration of prescription limited to 28 days.

The prescription must be written in full on a secure prescription pad.

Overlapping prohibited unless expressly stated by the prescriber on the prescription.

A copy of the prescription must be retained by the pharmacist for a period of 3 years.

Box of 28: 65% social security reimbursement. Approved for hospital use.

Box of 100: Approved for hospital use.

Price (excluding dispensing fee):

€7.10 (Box of 28 tablets in blister packs (Aluminium/PVC).

Daily cost of treatment: €0.51 to €0.76

Through the written commitments made by its Management team, Servier is committed to continuous quality improvement in the information it provides for solicitation or business development purposes for the promotion of medicinal products in accordance with the Charter signed by LEEM and CEPS and the certification guidelines issued by the French National Authority for Health (HAS).

The employee who has provided you with this document exercises his/her role in accordance with the ethics guidelines for organising meetings with health professionals, a copy of which (s)he can also provide. These regulations are also available on our website http://servier.fr in the "medicinal products" section.

Medical Information and Pharmacovigilance: Servier Medical Affairs - [name]- [contact] Assessment of the quality of the promotional information activities of our medical sales representatives: [contact] In the context of providing information for solicitation or business development purposes for the promotion of medicinal products, LES LABORATOIRES SERVIER, located at [name], are required to collect personal data about you. Pursuant to Articles 38 et seq. of law no. 78-17 of 6 January 1978 as amended, you can request access, rectify or object to the processing of this data by contacting us at the following email address: [contact].

18ST2229FF

3 Stablon Summary of Product Characteristics Certificate of Translation

UBIQUS UK LTD

Language Service Provider Certified ISO 9001:2008 Company Reg. No. 3444614

TRANSLATION CERTIFICATE

31/01/2019

Ubiqus UK certifies that we have translated your document from French into English to the best of our professional knowledge and belief for Quotient Sciences Limited, [name].

1. LIST OF ABBREVIATIONS

Table 1: List of Abbreviations

| Abbreviation | Term | |
|--------------|--|--|
| AE | adverse event | |
| AESI | adverse event of special interest | |
| BID | twice daily | |
| BMI | body mass index | |
| CFR | Code of Federal Regulations | |
| CGI-I | Clinician Global Impression of Improvement | |
| CGI-S | Clinician Global Impression of Severity | |
| CI | confidence interval | |
| СМН | Cochran-Mantel-Haenszel | |
| CRF | case report form | |
| CSFQ-14 | Changes in Sexual Functioning Questionnaire Short-Form | |
| CSR | clinical study report | |
| C-SSRS | Columbia Suicide Severity Rating Scale | |
| ECG | electrocardiogram | |
| EMA | European Medicines Agency | |
| ET | early termination | |
| FDA | Food and Drug Administration | |
| GCP | Good Clinical Practice | |
| ICH | International Council on Harmonization of Technical Requirements for Pharmaceuticals for Human Use | |
| IND | Investigational New Drug | |
| IRB | Institutional Review Board | |
| IP | Investigational product | |
| IU | international unit | |
| IWRS | interactive web response system | |
| LOE | lack of efficacy | |
| LS, LSM | least square, least square means | |
| mITT | modified intent-to-treat | |
| MedDRA | Medical Dictionary for Regulatory Activities | |
| MAR | missing at random | |

Tonix Pharmaceuticals Statistical Analysis Plan: TNX-TI-M201

[figure not shown]
| MCMC | Markov Chain Monte Carlo | |
|--------|---|--|
| MI | multiple imputation | |
| MMRM | Mixed-Effects Model of Repeated Measures | |
| NDA | New Drug Application | |
| NSAIDs | Non-steroidal anti-inflammatory drugs | |
| PGI-C | Patient Global Impression of Change | |
| PGI-S | Patient Global Impression of Severity | |
| QD | once daily | |
| SAE | serious adverse event | |
| SAP | statistical analysis plan | |
| SD | standard deviation | |
| SF | screen failure | |
| SOC | system organ class | |
| TEAE | Treatment-Emergent Adverse Event | |
| US | United States | |
| WHO-DD | World Health Organization Drug Dictionary | |

2. PURPOSE OF THE ANALYSES

This statistical analysis plan (SAP) describes the planned analysis and reporting for Protocol TNX-TI-M201 (A Phase 2, Randomized, Double-Blind, Placebo-Controlled, Parallel-Group Study to Evaluate the Efficacy, Safety, and Tolerability of TNX-601 ER Monotherapy versus Placebo in Patients with Major Depressive Disorder).

The structure and content of this SAP provides sufficient detail to meet the requirements identified by the US Food and Drug Administration (FDA), European Medicines Agency (EMA), and International Council for Harmonisation (ICH) of Technical Requirements for Registration of Pharmaceuticals for Human Use: Guidance on Statistical Principles in Clinical Trials. All work planned and reported for this SAP will follow internationally accepted guidelines for statistical practice, as published by the American Statistical Association and the Royal Statistical Society.

The planned analyses identified in this SAP may be included in clinical study reports (CSRs), regulatory submissions, or future manuscripts. Also, post-hoc exploratory analyses not necessarily identified in this SAP may be performed to further examine study data. Any post-hoc, or unplanned exploratory analysis performed will be clearly identified as such in the final CSR.

The reader of this SAP is encouraged to also read the clinical protocol, and other identified documents, for details on the planned conduct of this study. Operational aspects relating to collection and timing of planned clinical assessments are not repeated in this SAP unless they are relevant to the planned analysis.

3. PROTOCOL SUMMARY

This is a 6-week, randomized, double-blind, placebo-controlled, parallel-group, multicenter study to evaluate the efficacy, safety, and tolerability of TNX-601 ER, 39.4 mg monotherapy, on symptoms of depression in adult patients with MDD in approximately 30 sites in the United States. This study plans to randomize approximately 300 male and female patients aged 18 to 65 years old (inclusive), with current MDD as defined by DSM-5 criteria. During the 6-week double-blind treatment period, patients will receive either TNX-601 ER or placebo in a 1:1 randomization ratio. After the End of Treatment (Visit 5/ET), there will be a 2-week posttreatment safety follow-up period.

The study will be conducted in 4 periods: Screening (Visit 1), Baseline (Visit 2), Treatment (Visits 3-5), and Post Study Follow-up (Visit 6).

Screening (Visit 1)

Patients will be consented and assessed for current MDD as defined by DSM-5 diagnostic criteria, using the Mini International Neuropsychiatric Interview, Version 7.0.2 (MINI 7.0.2). Depression severity will be assessed by MADRS. Eligibility will also depend on medical history, physical and neurological examination, use of concomitant medications, and the results of laboratory tests (eg, pregnancy and drug screen, liver, kidney, and thyroid function, electrocardiogram).

If a patient meets all eligibility requirements but is currently taking a prohibited medication, there will be a Screening Period of up to 35 days for drug tapering and washout. For extenuating circumstances and in cases in which a prospective participant is on fluoxetine, the duration of the Screening Period may be increased to up to 49 days with Medical Monitor approval. Medication-free washout time for prohibited medications will be 4 weeks for antidepressants (except for fluoxetine, which will be 6 weeks) and atypical antipsychotics.

Baseline, Randomization, Start of Treatment (Visit 2)

To ensure continued eligibility prior to randomization, patients will be assessed for all inclusion/exclusion criteria, including a MADRS total score of \geq 25. Patient must also have a \leq 25% decrease or increase in MADRS score from Screening (Visit 1) to Baseline (Visit 2). Any patients not meeting these randomization criteria will be considered a Screen Failure (SF) and will not continue in the study. Eligible patients will be randomized in a 1:1 ratio to one of two treatment arms (once daily oral TNX-601 ER or placebo). At this visit, study drug will be dispensed, and the first dose will be given to eligible patients.

Double-Blind Treatment Period (Visits 3-5)

The Treatment Period will last for about 42 days. Several investigator- and patient-rated scales and safety assessments (eg, C-SSRS, AEs) will be administered at each visit. At each of the 3 visits, study drug compliance and accountability will be assessed by collecting previously dispensed study drug bottle and counting the remaining tablets.

Statistical Analysis Plan: TNX-TI-M201

All patients who withdraw early from the study will be encouraged to complete an Early Termination (ET) visit as early as possible for safety evaluations. The patients will also be strongly encouraged to come back for the Post Study Follow-up (Visit 6).

[figure not shown]
Post Study Follow-up (Visit 6)

Between discontinuation of study drug and the Post Study Follow-up (Visit 6), potential withdrawal effects will be assessed at home using the SOWS at +1 day, +2 days, +3 days, +6 days, +9 days, and +12 days after the End of Treatment (Visit 5/ET). This includes patients who are early terminated.

Approximately 14 days (+7 days) after discontinuation of study drug, all randomized patients will return to their respective study site for an off-drug, Post Study Follow-up (Visit 6). This visit will include an assessment of prior and concomitant medications, vital signs and weight, pregnancy test, AEs, C-SSRS, and the SOWS.

The overall duration in the study for each patient is expected to be up to 13 weeks.

Figure 1: Study Schema

The study timeline and events schedule are provided in Figure 1.

4. ANALYSIS SAMPLES

Three populations will be utilized for the analyses of data. Disposition of patients will use the All Patients Population. The safety analyses will be conducted on the Safety Population. The intention-to-treat (ITT) Population will be used for the efficacy analyses.

4.1. All Patients Population

This includes all patients available in the electronic data capture system; patients will be presented by their randomized treatments (if applicable).

4.2. Intention-to-Treat Population

The ITT population will include all randomized patients who receive at least 1 dose of the investigational product. The ITT population is the primary population for efficacy analyses and patients will be analyzed based on their randomized treatment.

4.3. Safety Population

The safety population will include all patients who received at least one dose of study drug. This population will be used to summarize the safety data. Patients will be analyzed according to their treatment received; if an error in issuing investigational product (IP) occurs and a patient receives a mix of treatments, they will be analyzed under the treatment arm with the most IP issued to the patient.

Statistical Analysis Plan: TNX-TI-M201

5. ESTIMANDS FOR PRIMARY AND KEY SECONDARY EFFICACY ENDPOINTS

5.1. Primary Efficacy

Population

The target population is individuals with major depressive disorder as defined by the inclusion/exclusion criteria.

Variable

The primary endpoint will be the change from Baseline (Visit 2) to Week 6 in the MADRS total score.

Intercurrent Events

Concomitant medications and all other intercurrent events other than discontinuation will use a treatment policy strategy; data will be analyzed as observed. A hypothetical strategy will be employed to handle intermittent missing data and discontinuation. Patients that that discontinue for adverse events or lack of efficacy will be assumed to be representative of patients that would not continue treatment and their values will be imputed with multiple imputation (MI) using the placebo distribution. All other missing values, whether intermittent or following discontinuation will be assumed to be missing at random and imputed with MI within treatment group. See section 9.1.1 for details of the imputation.

Population-Level Summary

The population-level summary will be the difference in least-square means between treatment arms (analyzed as randomized) at Week 6.

The primary efficacy analysis will use a mixed model repeated measures (MMRM) approach to estimate mean change from baseline to Week 6 in the MADRS total score visit in the TNX-601 ER and placebo arms. The model will include all patients in the ITT population, and the dependent variable will be the observed change from baseline in the MADRS total score at each post-randomization in-clinic visit. Covariates in the model will include the fixed categorical effects of treatment, site, visit, and treatment by visit interaction, as well as the continuous fixed covariates of baseline score and baseline score by visit interaction. Full details are given in section 9.1.2.

5.2. Key Secondary Efficacy

The efficacy endpoints listed below are considered key secondary endpoints.

- Change from Baseline (Visit 2) in the CGI-S score at Week 6
- Change from Baseline (Visit 2) in the SDS total score at Week 6

The key secondary efficacy endpoints will apply estimands parallel with the primary estimand, adjusted for the endpoint in question, but with identical populations and handling of intercurrent

Statistical Analysis Plan: TNX-TI-M201

events. MMRM methodology will be utilized for the continuous secondary endpoints, and analyses will be based on the ITT population. The dependent variable will be the observed change from baseline in the respective secondary endpoint at each post-randomization visit. Covariates in the model will include the fixed categorical effects of treatment, site, visit, and treatment by visit interaction, as well as the continuous fixed covariates of baseline score and baseline score by visit interaction.

6. STUDY PATIENTS

6.1. Disposition of Patients

The number and percentage of patients in each analysis population will be summarized. The number of patients screened, patients enrolled, and the number and percentage of patients completing the study, discontinuing from the study and reasons for discontinuation will also be reported. All percentages will be calculated using the number of patients enrolled as the denominator.

6.2. Demographic and Other Baseline Characteristics

Demographic and baseline characteristics such as age, gender, race/ethnicity, height, weight, BMI, and smoking history will be summarized by treatment group (TNX-601 ER and placebo) and overall for the ITT and Safety populations. Categorical items will be reported with counts and percentages; continuous items will be reported using summary statistics (mean, standard deviation (SD), median, minimum, maximum).

6.3. Prior and Concomitant Medications/ Therapies

Prior medications are defined as medications or therapies initiated prior to the start of the study drug and terminated prior to the start of study drug. Hence, these medications or therapies will have end dates prior to the first dose date of study drug. Concomitant medications are defined as any medications other than the study drug that a patient receives concurrently with the study drug. These medications will have end dates on or after the first dose date of the study drug if they have an end date. In the case of missing or partial dates, medications will be considered concomitant unless the available data excludes that possibility.

All medications will be coded using the World Health Organization Drug Dictionary (WHO-DD). Prior and concomitant medications will be summarized by treatment group and by the number and percentage of patients taking each medication, classified by using WHO-DD Anatomical Therapeutic Chemical Level 3 and preferred term.

Prior medications for MDD are collected on a separate case report form including whether the patient had an efficacy response to the drug and how well they tolerated the drug. Prior MDD drugs will be summarized by preferred term and response; and by preferred term and tolerability.

Prior psychotherapy will be collected at the screening visit. The count and percentage of patients receiving each type of therapy will be summarized by treatment for each prior therapy; this will also be reported for each therapy flagged as ongoing. All psychotherapy will be presented in a listing including the reported start and stop dates of the therapy.

All medications and therapies will be presented in listings, with prior MDD medications and therapies listed separately.

Statistical Analysis Plan: TNX-TI-M201

6.4. Medical History and Physical Examination

Medical History will be coded using the Medical Dictionary for Regulatory Activities (MedDRA) and summarized by system organ class (SOC) and Preferred Term using frequency counts and percentages by treatment group. Physical examination findings will be presented in listings.

7. STUDY OPERATIONS

7.1. Protocol Deviations

A protocol deviation is any noncompliance with the clinical trial protocol or ICH Good Clinical Practice (GCP) requirements. The noncompliance may be either on the part of the patient, the investigator, or the study site staff. As a result of deviations, corrective actions are to be developed by the site and implemented promptly. Protocol deviations will be logged and categorized as important or non-important prior to unblinding. Protocol deviations will be summarized by type, status as important/non-important, and by treatment group for the Safety population.

Individual protocol deviations will be listed by patient.

7.2. Randomization

This is a double-blind study; unless otherwise specified, all study personnel are to remain blinded to study drug prior to database lock and final analysis following study unblinding.

A total of approximately 300 patients will be randomized in a 1:1 ratio to treatment with once-daily oral TNX-601 ER (tianeptine hemioxalate extended-release tablets) or identical placebo tablets, which are devoid of the tianeptine hemioxalate but contain the same inactive ingredients present in the active tablets. Randomization will be stratified by study site.

The randomization schedule will be computer generated using a permuted block algorithm and will randomly allocate study drug to randomization numbers. The randomization numbers will be assigned through a central interactive web response system (IWRS) as patients are entered into the study.

7.3. Measures of Treatment Compliance

The treatment duration will be calculated and summarized based on CRF data for first and last dose dates (number of days=last dose date – first dose date+1).

Days of exposure will be based on drug accountability and the number of tablets taken assuming once daily dosing. The number of patients with total exposure by visit weeks (\leq 2 weeks, 2 to \leq 4, 4 to \leq 6, and \geq 6 weeks) will be presented.

Compliance will be similarly summarized across all study visits and overall for each treatment arm. Study drug compliance as a percentage will be defined as the exposure days defined above divided by the total number of expected days on treatment multiplied by 100. The expected number of days will be the drug return date-drug issue date +1 for individual visits and the treatment duration as defined above for the overall compliance.

Compliance will be summarized with descriptive statistics by treatment arm. The number and percentages of patients within certain categories of compliance (e.g. < 60%, 60% to < 80%, 80% to $\le 100\%$, greater than 100%) will also be presented.

Tonix Pharmaceuticals Statistical Analysis Plan: TNX-TI-M201

A listing of drug accountability data based on CRF data will be provided.

Statistical Analysis Plan: TNX-TI-M201

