9. STUDY DRUG MATERIALS AND MANAGEMENT

9.1. Study Drug Packaging, and Labeling and Storage

Study drug supplies will be packaged identically so as to maintain the integrity of the study blind. The study drug bottles will be labeled minimally with the following information: study number TNX-TI-M201, sponsor name and address, bottle number, quantity, storage conditions, usage instructions, and caution statements for investigational new drug, eg, Caution: New Drug – Limited by United States Law to Investigational Use and Keep Out of Reach of Children and Pets.

Each study drug bottle will contain 20 tablets. One bottle will be dispensed to each patient at Visit 2 (Baseline), Visit 3 (Week 2), and Visit 4 (Week 4); this will provide the patient with 20 tablets to cover the 2 weeks of dosing between visits, plus additional tablets to cover loss

and/or visit window variability. The patient should be instructed to keep this study drug in a safe location out of extreme environmental conditions and out of the reach of children and pets, and that this drug is not to be taken by any individual other than the study patient. Each patient will also be instructed that they will be expected to return the bottle and all unused study drug at each clinic visit; unused drug will be counted to assess compliance with study drug treatment.

Storage of the study drug at the investigational sites should be under locked and secure conditions with limited staff access. Study drug should be stored at 15-25°C/59-77°F in a temperature/humidity-monitored room.

9.2. **Dosing Instructions**

Patients will be instructed to take one tablet of their assigned study drug (TNX-601 ER or placebo) orally, each morning and continuing without interruption for 6 weeks. Day 1 study drug will be taken in the clinic. They should swallow the tablets whole, and not crush or chew the tablets. The tablet should be taken in the morning with breakfast. Patients will be reminded that only 1 tablet is allowed per day. Note: In the event that the patient misses a dose, instruct the patient to continue dosing with one (1) tablet the next morning; eg, they should not take more to make up for the missed dose.

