9.5. Study Drug Accountability and Reconciliation

All patients will be expected to bring their bottle of study drug with them to all study visits. At each study visit, the site staff will inspect the drug bottle, and perform a count of the tablets

remaining in the bottles and document this in the patient's record. An assessment of drug adherence should be done by the study staff to ensure that the patient understands all dosing instructions and is taking the drug as prescribed. Patients will be asked for an explanation if the count of returned study drug tablets indicates a discrepancy between the expected number of tablets dosed and the number returned in the bottle. If it is found that the patient is not taking the study drug as expected, the patient will be re-counselled with instructions, and this should be noted in the patients' records. A deviation should be recorded on any patient who is less than 70% compliant with dosing between visits.

If the patient fails to return any of the unused study drug as expected, the Investigator will identify if it matches a MADDERS[®] triggering event and complete the MADDERS[®] Supplemental Drug Accountability Form. Patient should be evaluated by the Investigator for the reason for the lower-than-expected tablet number and about potential misuse, abuse, or diversion, and the Investigator will address this accordingly. If more than 1 tablet cannot be accounted for at any of the visits where drug is returned (Week 2, 4, or 6), the Investigator will be asked to evaluate the situation, and a written summary of this evaluation should be added to the source and entered onto the case report form (CRF). Situations where replacement drug is requested, or when more than 1 tablet cannot be accounted for, should be recorded as deviations.

All study drug, including partial and empty bottles, must be maintained at the study site until Tonix or its designee verifies drug accountability and provides instruction for destruction or the return of the investigational product to the Sponsor's drug distribution depot.

Tonix or their designee will perform drug accountability which entails reconciliation between the amount of drug shipped to the study site, study drug assigned and dispensed to the patient (including returned unused assigned study drug), and study supplies that were never dispensed and/or assigned to patients.

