10.3. Visits 3 and 4 (Weeks 2 through 4)

Visits 3 and 4 are similar study visits that are scheduled to be conducted after 2 and 4 weeks of treatment, respectively. Visit 3 should occur on Day 15 ± 2 days and Visit 4 should occur on Day 29 ± 2 days.

The following assessments and procedures are scheduled for these visits in the following general order:

- Collect study drug and assess compliance and accountability
- Assess occurrence of AEs
- Update concomitant medications
- Obtain vital signs and weight
- Review placebo response training with patient
- Administer the MADRS
- Conduct urine pregnancy test (for women of child-bearing potential)
- Visit 4 only: Draw samples, fasting or non fasting, for clinical laboratory tests for:
 - Chemistry and hematology
 - o PK
- Have the patient complete the following outcome scales (in order):
 - o SDS
 - o PGIS
 - o PGIC
- Administer the HARS
- Administer C-SSRS Since Last Visit Version
- Administer MADDERS[®] only if any pre-defined AEs and/or Drug Accountability Discrepancy Events (DADE) suspect for misuse, abuse, or diversion event is identified
- Investigator to assess CGI-S and CGI-I (needs to be completed once all other assessments are available for Investigator to review)

• Dispense new bottle of double-blind study drug as assigned by IWRS

After all assessments at each visit have been completed, the patient should be given an appointment to return to the clinic for the next scheduled visit, and be re-instructed, as necessary, on dosing instructions, and reminded to bring study drug back to the clinic at their next visit.

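### SAP 7.3 counts each bottle hand-over day twice in per-visit compliance, so a fully adherent patient reads below 100% in at least one interval; separately, 42 days of exposure fits two bins

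*SAP*

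**What the plan says.** SAP 7.3 (Measures of Treatment Compliance) divides exposure days by expected days. The numerator is a tablet count: "Days of exposure will be based on drug accountability and the number of tablets taken assuming once daily dosing". The denominator has two forms. For single intervals, "The expected number of days will be the drug return date-drug issue date +1 for individual visits". For the whole study it is "the treatment duration as defined above for the overall compliance", that is, last dose date minus first dose date plus 1.

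The same section tabulates exposure: "The number of patients with total exposure by visit weeks". As the text available to us reads, the last two bins run from 4 up to and including 6 weeks, and from 6 weeks upward.

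The protocol fixes the calendar. Section 10.3 places return and re-issue at the same visit: "Collect study drug and assess compliance and accountability" comes first in its list and "Dispense new bottle of double-blind study drug as assigned by IWRS" comes last. Section 9.2 allows one tablet a day for 6 weeks: "The tablet should be taken in the morning with breakfast". Neither document says which bottle supplies the tablet on a visit day, and the SAP has no rule for that shared day.

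**The concern.** Adding 1 to a difference of dates is right for a single closed interval. It is not right for adjoining intervals that share an end day, because each shared day is then counted twice. The three per-visit denominators add up to more days than the patient could have dosed. The interval figures then disagree with the overall figure for the same patient and the same tablets.

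At stake is the accuracy of the visit-level compliance summaries. Taken over the three intervals together they run low, in both arms alike. A surplus tablet in one interval can also be masked. In the exposure table, a patient at exactly the planned treatment length has two possible rows, and the programmer must choose between them without a stated rule.

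**Working it through.** **Inputs.** First issue and first dose are on Day 1 (Protocol 10.2.2). Visit 3 is Day 15 ± 2 and Visit 4 is Day 29 ± 2 (10.3). Visit 5 is Day 43 + 2 (10.4). One tablet is taken per day (9.2). The plan's own length of about 42 days (7.1) is reproduced by 43 − 1 = 42.

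**Denominators as written, nominal visits.** (15 − 1 + 1) + (29 − 15 + 1) + (43 − 29 + 1) = 15 + 15 + 15 = 45. The overall denominator is 42 − 1 + 1 = 42 if the last dose is on Day 42, or 43 − 1 + 1 = 43 if it is on Day 43.

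**Full adherence, every bottle source.** The Day 15 and Day 29 tablets may each come from the old or the new bottle, and the last dose may be on Day 42 or 43. This gives eight patterns:

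| Day 15 / Day 29 source | Last dose | Tablets per bottle | As written (%) |
|---|---|---|---|
| new / new | 42 | 14, 14, 14 | 93.3, 93.3, 93.3 |
| new / new | 43 | 14, 14, 15 | 93.3, 93.3, 100 |
| new / old | 42 | 14, 15, 13 | 93.3, 100, 86.7 |
| new / old | 43 | 14, 15, 14 | 93.3, 100, 93.3 |
| old / new | 42 | 15, 13, 14 | 100, 86.7, 93.3 |
| old / new | 43 | 15, 13, 15 | 100, 86.7, 100 |
| old / old | 42 | 15, 14, 13 | 100, 93.3, 86.7 |
| old / old | 43 | 15, 14, 14 | 100, 93.3, 93.3 |

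Every pattern has at least one interval below 100%, and seven of the eight have two or more. Pooled over intervals, the patient reads 42/45 = 93.3% or 43/45 = 95.6%. Overall compliance is 100% throughout.

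**Visit windows.** For visits on Days V3, V4 and V5 the three denominators sum to V3 + (V4 − V3 + 1) + (V5 − V4 + 1) = V5 + 2.

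- *Dosing runs to Visit 5 or the day before.* Doses are V5 or V5 − 1, so the excess is 2 or 3 days. The lowest interval value is the middle one with V3 = 17 and V4 = 27. If Day 17 comes from the old bottle and Day 27 from the new, Days 18 to 26 give 9 tablets over 27 − 17 + 1 = 11 days, or 81.8%.
- *Dosing stops after 42 doses and Visit 5 is on Day 44 or 45.* The excess is 46 − 42 = 4 or 47 − 42 = 5 days. With V4 = 31, V5 = 45 and the Day 31 tablet from the old bottle, Days 32 to 42 give 11 tablets over 45 − 31 + 1 = 15 days, or 73.3%. That falls in the 60% to below 80% category.

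**Patients who are not exactly adherent.** With 14 possible doses, 15 tablets is 15/14 = 107.1% but prints as 15/15 = 100%. With 13 possible doses, 11 tablets is 84.6% but prints as 11/15 = 73.3%, which crosses the 80% limit. At 14 possible doses neither the 60% nor the 80% limit is crossed: 9/15 = 60.0% and 12/15 = 80.0% still qualify.

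**Exposure bins.** 42/7 = 6.0 weeks, which satisfies both the closed upper limit of one bin and the closed lower limit of the next.

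**The case against.** The best counter-argument concerns the remedy. Morning dosing with breakfast, and a new bottle handed over at the end of the visit, suggest that the visit-day tablet may come from the old bottle. If so, the first-interval formula is exactly right (15/15). A denominator that gives the shared day to the new bottle would then show 15/14 = 107.1% there. Under that rule six of the eight patterns have one interval at 107.1%, whereas the current formula shows a fully adherent patient above 100% in none. In a study that tracks misuse and tablet discrepancies, spurious readings above 100% are unwelcome.

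This stands as a reason to state the convention and its limitation. It does not rescue the formula: the denominators exceed the doses whatever the bottle source, whereas the one-tablet error under the corrected rule cancels across intervals.

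The effect is also small. The compliance categories are given only as examples, no planned table is said to pool a patient's three intervals, and the overall denominator is sound. All of that stands.

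Three stronger readings are tempting, and the documents do not support them:

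- *Every interval is biased low.* It is not; single intervals can read a correct 100%.
- *Protocol deviations will be misrecorded.* Protocol 9.5 says "A deviation should be recorded on any patient who is less than 70% compliant with dosing between visits". If the site expects 14 doses, 10 tablets is 71.4%, while the SAP prints 10/15 = 66.7%. But Protocol 9.5 gives no formula and the site makes the count, so the SAP table changes no recorded deviation.
- *Over-use is concealed.* Surplus tablets still appear in the Protocol 9.5 counts and in the SAP's accountability listing.

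**Conclusion.** The point holds and is minor. SAP 7.3's two denominators cannot both be right for the same patient, and the per-visit one is at fault. The bottle source does not affect that conclusion. The lowest fully adherent value does depend on when dosing ends, which the documents leave open: Protocol 9.2 describes 6 weeks, Visit 5 may fall as late as Day 45, and Protocol 9.1 supplies spare tablets for visit-window variability. It would therefore be too much to say that a fully adherent patient always stays at 80% or above.

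The bin overlap at 42 days is real as the text reads, but the sign was read from a PDF by a program and should be checked against the original.

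No efficacy analysis uses these values, and none of the populations in SAP section 4 is defined by compliance.

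**What to change.** Count each dosing day once and end the last interval at the last dose date, so that the interval denominators sum to the SAP's treatment duration. For example, use return date minus issue date for each bottle followed by another, and last dose date minus issue date plus 1 for the last bottle used. At nominal visits this gives 14 + 14 + 14 = 42 or 14 + 14 + 15 = 43.

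State the bottle convention for the visit-day tablet. State also that where the actual bottle differs or is unknown, a fully adherent patient's interval can be off by one tablet in either direction: 13/14 = 92.9% or 14/15 = 93.3% on the low side, 15/14 = 107.1% on the high side. A one-tablet excess in a single interval should then be read against overall compliance.

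Define the exposure bins in days, without overlap and with completers together, for example ≤14, 15–28, 29–41 and ≥42 days. Starting the top bin above 6 weeks would also remove the overlap, but it would separate a 42-day completer from one who took a Day 43 tablet.

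The cost is a few lines of SAP text and a small programming change, with no new data. The drawback is that single-interval values can err by one tablet either way, in place of a systematic shortfall.
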